6.1.5 Overdosage

Overdose is not anticipated in the context of a clinical trial. Subjects will be given the subcutaneous injection every other day and daily infusions of remdesivir. No study product will be given after hospital discharge.

6.2 Preparation/Handling/Storage/Accountability

6.2.1 Acquisition and Accountability

Investigational products (IP) will be shipped to the site either directly from participating companies, from the Sponsor, or from other regional or local drug repositories. All other supplies should be provided by the site. Multiple lots of each IP may be supplied.

Study products received at the sites will be open label and not kit specific, unless specified in the protocol-specific Manual of Procedures (MOP) or pharmacy manual. See the MOP Appendices for detailed information on the preparation, labeling, storage, and administration of investigational products.

Accountability:

The site PI is responsible for study product distribution and disposition and has ultimate responsibility for study product accountability. The site PI may delegate to the participating site's research pharmacist responsibility for study product accountability. The participating site's research pharmacist will be responsible for maintaining complete records and documentation of study product receipt, accountability, dispensation, storage conditions, and final disposition of the study product(s). Time of study drug administration to the subject will be recorded on the appropriate data collection form (CRF). All study product(s), whether administered or not, must be documented on the appropriate study product accountability record or dispensing log. The Sponsor's monitoring staff will verify the participating site's study product accountability records and dispensing logs per the site monitoring plan. Refer to the protocol-specific MOP for details on storing study medications.

Destruction:

After the study treatment period has ended or as appropriate over the course of the study after study product accountability has been performed, used active and placebo product can be destroyed on-site following applicable site procedures with a second staff member observing and verifying the destruction.

Unused product at the end of the study should be saved until instructed by the Sponsor.

6.2.2 Formulation, Appearance, Packaging, and Labeling

Remdesivir component

Remdesivir may be supplied in two formulations:

- The lyophilized formulation of remdesivir is a preservative-free, white to off-white or yellow, lyophilized solid containing 150 mg or 100 mg of remdesivir to be reconstituted with 29 mL or 19 mL (respectively) of sterile water for injection respectively and diluted into IV infusion fluids prior to IV infusion. Following reconstitution, each vial contains a 5 mg/mL remdesivir concentrated solution with sufficient volume to allow withdrawal of 30 mL (150 mg of remdesivir) or 20 mL (100 mg of remdesivir). It is supplied as a sterile product in a single-use, Type 1 clear glass vial. In addition to the active ingredient, the lyophilized formulation of remdesivir contains the following inactive ingredients: water for injection, SBECD, hydrochloric acid, and/or sodium hydroxide. For more information, refer to the MOP.

- The concentrated solution is supplied as a single dose vial containing 100 mg/20 mL (5 mg/mL) of remdesivir per vial for dilution into 0.9% sodium chloride infusion bag. It is a sterile, preservative-free, clear, colorless to yellow, aqueous-based concentrated solution that is to be diluted into 0.9% sodium chloride infusion bag prior to administration by intravenous infusion. Remdesivir injection, 100 mg/20 mL (5 mg/mL), is supplied in a single-dose clear glass vial. For more information, refer to the MOP and EUA Fact Sheet.

Remdesivir will be labeled according to manufacturer specifications.

Subcutaneous Interferon beta-1a component

Rebif® (interferon beta-1a) is formulated as a sterile solution. It is supplied as a prefilled syringe intended for subcutaneous injection. Each prefilled syringe contains 0.5 mL of Rebif®. Each 0.5 mL of Rebif® will contain 44 mcg of interferon beta-1a, 4 mg human albumin, USP; 27.3 mg mannitol, USP; 0.4 mg sodium acetate; and water for injection, USP.

Subcutaneous placebo component

Placebo will match the active product in appearance. Placebo subcutaneous injection is 0.9% normal saline. The placebo will be supplied as either:

- Matching empty syringes that will be filled with approximately 0.5 mL 0.9% normal saline at each site pharmacy; OR
- Matching syringes prefilled with 0.5 mL 0.9% normal saline or 0.5 mL sterile water for injection.

Study products will be supplied by the sponsor or its designee in accordance with current Good Manufacturing Practice (cGMP).

6.2.3 Product Storage and Stability

The MOP provides instructions for the preparation, handling, and storage of remdesivir. The MOP describes site responsibility and accountability for the administered products. Interferon beta-1a drug product will be described in the package insert. See most recent version of package insert posted on the Emmes website.

6.2.4 Preparation

Refer to the protocol-specific MOP for details about preparation.

Remdesivir is not considered a hazardous drug as defined by NIOSH and ASHP hazard classification systems. The study products may be prepared in a clean room but do not need to be prepared or handled in a fume hood. Measures that minimize drug contact with the body should always be considered during handling, preparation, and disposal procedures as indicated in the Package Insert.

6.3 Measures to Minimize Bias: Randomization and Blinding

6.3.1 Randomization

Randomization will be stratified by:

- Site
- Severity of illness at enrollment (by ordinal scale)
 - Hospitalized, requiring supplemental oxygen, or
 - Hospitalized, not requiring supplemental oxygen.

Note: Category 7 (hospitalized, on invasive mechanical ventilation/ECMO) and Category 6 (hospitalized, on non-invasive ventilation or high flow oxygen devices) are not eligible for enrollment. See description of recommendations made by the DSMB on September 4, 2020 below.

The randomization procedure will be described in the MOP.

There was the hypothetical concern that interferon may worsen the pro-inflammatory state seen in COVID-19 late in the clinical course of the disease. For this reason, enrollment was staged based on severity of disease.

- For the first 2 weeks of the study, enrollment was limited to non-intubated, hospitalized COVID-19 patients who meet all eligibility criteria (i.e., patients with baseline ordinal scale score of 4, 5 or 6).
- On September 4, 2020, the DSMB met for an interim safety review of the ACTT-3 data. After their review, they notified NIAID that their recommendation was to close further enrollment to patients with a baseline ordinal score of 6. The DSMB noted there was no increase in mortality in this group, but that the risk/benefit in this group did not warrant further enrollment. Specifically, it was recommended by the DSMB:
 - No further enrollment of subjects with ordinal score of 6 at time of randomization.
 - Do not enroll subjects with ordinal score of 7 at time of randomization
 - Continue to enroll patients with a baseline ordinal score of 4 and 5.
- Furthermore, the DSMB recommended:
 - Subjects currently enrolled who have an ordinal score of 6, should not be given any more study injections (interferon/placebo) for the remainder of the study.
 - Subjects enrolled as a baseline ordinal 4 or 5 and remain as ordinal 4 or 5, should continue to receive study injections (interferon/placebo) and remdesivir per protocol.
 - If a subject is enrolled as a baseline ordinal 4 or 5 and progresses to ordinal 6 or 7, the study injections (interferon/placebo) should be discontinued for the remainder of the study. In this case, the remdesivir infusions would continue per protocol.

Importantly, all subjects should remain in the study and followed through day 29 in accordance with the protocol.

6.3.2 Blinding and Masking Procedures

As both arms are receiving remdesivir, the remdesivir product is not blinded and study infusions can be labeled accordingly.

The subcutaneous interferon beta-1a/matching placebo component is blinded. Interferon beta-1a and placebo will be identical in appearance.

Unblinding of the study will occur after all subjects enrolled have reached the end of study, and these visits are monitored and data is cleaned, or if the DSMB recommends unblinding.

Treatment group-level unblinded analyses of subjects randomized in ordinal score category 6 may be conducted and published prior to the end of the trial to communicate the safety signal observed in this group by the DSMB during a safety review. If this analysis is conducted, only members of the unblinded analysis team will have access to subject-level treatment data while the study is ongoing; all other members of the study group will remain blinded to individual subject treatments as originally planned.

If AEs occur and investigators are concerned about the treatment allocation, the treatment can be discontinued. If a Serious Adverse Event occurs, that is thought to be related to the study drug, and the treating clinician believes that knowledge of the treatment arm may change the therapy provided to the patient, the individual subject can be unblinded. The procedure for unblinding will be further detailed in the Manual of Operations.

6.4 Study Intervention Compliance

Each dose of study product will be administered by a member of the clinical research team who is qualified and licensed to administer the study product. Administration and date, and time, will be entered into the case report form (CRF).

6.5 Concomitant Therapy

6.5.1 Permitted Concomitant Therapy and Procedures

Receipt of any exclusionary treatments or medications prior to screening will be assessed at screening to determine eligibility as described in the exclusion criteria. Exclusionary medications include the receipt of convalescent plasma or intravenous immunoglobulin (IVIg) for the treatment of COVID-19. It also includes small molecule tyrosine kinase inhibitors (e.g., baricitinib, imatinib, gefitinib, acalabrutinib) or monoclonal antibodies targeting cytokines (e.g., TNF inhibitors, anti-interleukin-1 [IL-1], anti-IL-6 [tocilizumab or sarilumab]), or T-cells or B-cells, taken in the two weeks prior to screening for the treatment of COVID-19. Lastly, those who received interferon within 2 weeks of screening either for the treatment of COVID-19 or for a chronic medical condition (e.g., multiple sclerosis, HCV infection) will not be eligible for the study.

Appendix C - ACTT-3: Remdesivir + Interferon Beta-1a

For patients that are eligible for the study, other therapy received prior to enrollment with any other experimental treatment or off-label use of marketed medications that are intended as specific treatment for COVID-19 or the SARS-CoV-2 infection (i.e., post-exposure prophylaxis [PEP]) are permitted but must be discontinued on enrollment. There is no waiting period between discontinuation of these treatments and administration of study products. However, these prior treatments and their end date should be documented on the Concomitant Medication (CCM) form in the Advantage eClinical system.

Medications used for other non-COVID-19 diseases that also are claimed to be treatments for COVID-19, do not need to be discontinued at the time of enrollment. Examples would include lopinavir/ritonavir for HIV, hydroxychloroquine for lupus, etc. The disease being treated is important: if used as an off-label medication for COVID-19 treatment, they are prohibited; if used for non-COVID-19 diseases, they are allowable.

6.5.2 Prohibited Concomitant Therapy

A subject cannot participate in another clinical trial for the treatment of COVID-19 until after Day 29 (see exclusion criteria).

Once enrolled, concomitant medications for the treatment of COVID-19 as described in written policy or guideline (i.e., not just an individual clinician decision) are permitted. In the absence of a local written standard of care, the National Institutes of Health (NIH) COVID-19 Treatment Guidelines may be used (<https://www.covid19treatmentguidelines.nih.gov/>). This includes anti-inflammatory medications such as dexamethasone and convalescent plasma. Concomitant use of any other experimental treatment or off-label use of marketed medications intended as specific treatment for COVID-19 or SARS-CoV-2 infection, and not specified in the local or NIH COVID-19 Treatment Guidelines are prohibited. Specifically, use of any biologic therapy not specified on the written policy or guideline are prohibited including: monoclonal antibodies targeting cytokines (e.g., TNF inhibitors; interleukin-1[IL-1], IL-6 [tocilizumab or sarilumab]), or T-cells (e.g., abatacept); monoclonal antibodies targeting B-cells (e.g., rituximab, and including any targeting multiple cell lines including B-cells); JAK inhibitor(s) (e.g., baricitinib, imatinib, gefitinib, acalabrutinib); and any type of interferon, convalescent plasma, or immunoglobulin (IgG) therapies for COVID-19. Similarly, the concomitant use of hydroxychloroquine to treat COVID-19 is prohibited unless it is included in the local institutional treatment guidelines.

On August 23, 2020, the FDA issued an EUA for COVID-19 convalescent plasma for the treatment of hospitalized patients with COVID-19. The NIH COVID-19 Treatment Guidelines were updated on September 1, 2020 and concludes that “there are insufficient data to recommend either for or against the use of convalescent plasma for the treatment of COVID-19”. According to the NIH Guidelines and the EUA Fact Sheet for Health Care Providers, convalescent plasma should not be considered the standard of care for the treatment of patients with COVID-19. However, if a site has adopted convalescent plasma as part of their institutional standard of care for the treatment of COVID-19 patients, it is allowed as described above.

Concomitant medications will be assessed from 7 days prior to enrollment to Day 29 or upon discharge, whichever comes first. All prescription medications should be recorded during this

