5.2 Exclusion Criteria

1. Anticipated discharge from the hospital or transfer to another hospital which is not a study site within 72 hours.
2. Subject meets criteria for ordinal scale category 6 or 7 at the time of screening.
3. Subject has a positive test for influenza virus during this current hospital admission.
4. Subjects with an estimated glomerular filtration rate (eGFR) < 30 mL/min are excluded unless in the opinion of the PI, the potential benefit of receiving remdesivir outweighs the potential risk of study participation.
5. ALT or AST > 5 times the upper limits of normal.
6. Total white cell blood cell count (WBC) < 1500 cells/ μ L.
7. Platelet count < 50,000/ μ L.
8. History of chronic liver disease (e.g., jaundice, ascites, hepatic encephalopathy, history of bleeding esophageal or gastric varices). No laboratory testing is needed.
9. Pregnancy or breast feeding (lactating women who agree to discard breast milk from Day 1 until three weeks after the last study product is given are not excluded).
10. Allergy to any study medication including history of hypersensitivity to natural or recombinant interferon beta or human albumin.
11. Patient has a chronic or acute medical condition or is taking a medication that cannot be discontinued at enrollment, that in the judgement of the PI, places them at unacceptable risk for a poor clinical outcome if they were to participate in the study.
12. Received three or more doses of remdesivir, including the loading dose, outside of the study for COVID-19.
13. Received convalescent plasma or intravenous immunoglobulin [IVIg]) for the treatment of COVID-19.
14. Received any interferon product within two weeks of screening, either for the treatment of COVID-19 or for a chronic medical condition (e.g., multiple sclerosis, HCV infection)
15. Received any of the following in the two weeks prior to screening as treatment of COVID-19:
 - small molecule tyrosine kinase inhibitors (e.g. baricitinib, imatinib, gefitinib, acalabrutinib, etc.);
 - monoclonal antibodies targeting cytokines (e.g., TNF inhibitors, anti-interleukin-1 [IL-1], anti-IL-6 [tocilizumab or sarilumab], etc.);
 - monoclonal antibodies targeting T-cells or B-cells as treatment for COVID-19
16. Prior enrollment in ACTT-3

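### ACTT-3 bans off-study interferon after enrollment only where no written policy or guideline lists it, so local policy could allow the investigational drug open-label in either arm

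*Protocol*

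**What the plan says.** All references are to Appendix C (ACTT-3) of the protocol unless stated otherwise.

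Section 6.5.2 opens by barring participation in another COVID-19 treatment trial until after Day 29. It then permits, once a subject is enrolled, "concomitant medications for the treatment of COVID-19 as described in written policy or guideline", with the NIH guideline available where no local written standard exists. The prohibition that follows is tied to the same condition: "use of any biologic therapy not specified on the written policy or guideline are prohibited including" a list that ends with "any type of interferon, convalescent plasma, or immunoglobulin (IgG) therapies for COVID-19".

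The same section says that "the concomitant use of hydroxychloroquine to treat COVID-19 is prohibited unless it is included in the local institutional treatment guidelines". It allows convalescent plasma "if a site has adopted convalescent plasma as part of their institutional standard of care".

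Before enrollment the rule has no such condition. Exclusion criterion 14 (section 5.2) removes anyone who "Received any interferon product within two weeks of screening, either for the treatment of COVID-19 or for a chronic medical condition". Section 6.5.1 says that other prior COVID-19 therapies "are permitted but must be discontinued on enrollment".

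Sections 6.3.1 and 7.1.1.2 stop the study injections for the rest of the study once a subject reaches category 6 or 7.

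On recording, section 6.5.2 says: "Concomitant medications will be assessed from 7 days prior to enrollment to Day 29 or upon discharge, whichever comes first". All prescription medications are recorded apart from listed exempt classes, and biologics may not use the option of recording a drug only once.

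**The concern.** Interferon plus remdesivir against placebo plus remdesivir is the only contrast ACTT-3 tests. A rule that leaves it to a site's written policy whether controls may receive interferon lets something outside the protocol narrow that contrast. Dilution of this kind costs power; it does not raise the type I error.

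There is also a safety side. The DSMB recommended ending enrollment in category 6 and stopping injections on progression to category 6 or 7, and the synopsis suggests that interferon may have increased inflammation in category 6. Because the stopping rule is written for study injections, it does not reach the same drug given off-study to the same patients.

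**Working it through.** **Step 1: is the condition operative?** Convalescent plasma sits in the same list item as interferon, and section 6.5.2 expressly allows it where a site has adopted it. Hydroxychloroquine is introduced as a parallel case and is banned only when local guidelines omit it. The list is therefore a ban with a policy exception, and interferon falls under that exception.

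**Step 2: does anything else close the gap after randomization?**

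- Exclusion criterion 14 is unconditional but covers only the two weeks before screening.
- Section 6.5.1, first part, requires earlier COVID-19 therapy to stop at enrollment. It does not govern therapy started later under 6.5.2.
- Section 6.5.1 also says that drugs for other diseases are prohibited if used off-label for COVID-19. That passage concerns drugs in use at enrollment, and its own example, hydroxychloroquine, is allowed under local guidelines in 6.5.2. It cannot be read as an absolute ban without contradicting 6.5.2.
- Sections 6.3.1 and 7.1.1.2 stop study injections only.
- Inclusion criterion 8 (5.1), section 5.4 and the first sentence of 6.5.2 bar other COVID-19 treatment trials. That closes the trial route, but not policy-based use outside a trial.

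**Step 3: comparison with ACTT-4.** Appendix D 6.5.2 keeps a similar policy-dependent list, which names baricitinib. It first prohibits off-study baricitinib, dexamethasone and other glucocorticoids directly, with stated exceptions. Appendix D 6.5.4 makes such use outside category 7 a protocol deviation, again with a stated exception. ACTT-3 has no counterpart for interferon.

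**Step 4: size, for illustration.** Inputs from section 9.2: recovery rate ratio 1.25, two-sided alpha 0.05, 85% power, 723 recoveries needed, 831 planned.

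The plan's own figure first: E = 4(1.96 + 1.0364)² / (ln 1.25)² = 4 × 8.978 / 0.04979 ≈ 722, against 723 stated, so it reproduces.

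Suppose a share c of the log ratio is lost. Both c and this shrinkage rule are assumptions, since the protocol gives no rate of off-study interferon. Then power = Φ[(1 − c) × ln(1.25) × √(E/4) − 1.96]. At E = 831, ln(1.25) × √207.75 = 0.2231 × 14.41 = 3.216.

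| c | Diluted ratio 1.25^(1−c) | Power, 831 recoveries | Power, 723 recoveries |
|---|---|---|---|
| 0 | 1.25 | 89.6% | 85.1% |
| 5% | 1.24 | 86.3% | 81.3% |
| 10% | 1.22 | 82.5% | 77.0% |
| 20% | 1.20 | 73.0% | 67.0% |

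The largest c that keeps 85% power at 831 recoveries is 1 − (1.96 + 1.0364)/3.216 = 0.068, or about 6.8%.

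Two limits apply. If c is read as the fraction of controls treated, the table is pessimistic, because it gives each of them the full interferon effect from Day 1. It also assumes that interferon helps the recipient, so it does not describe use in category 6 or 7, where the protocol suspects the opposite. Section 9.2 attributes the increase from 723 to 831 to lower efficacy in the sicker stratum, so that margin was not set aside for contamination.

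**The case against.** The strongest reply is that the gap may be empty in practice. Interferon for COVID-19 appears in this protocol only as a trial or study treatment, and the trial route is closed. Section 6.5.2 rules out an individual clinician's choice, so the default is prohibition with interferon named. The gap opens only if a written policy or guideline lists interferon, and no passage shows one that does. All of this stands, and it limits the point to non-trial, policy-based use.

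A second reply is that ACTT-4 needed a direct ban more plainly: both its agents had shown efficacy in large trials and were available outside the trial. That also stands. The comparison shows that the sponsor has a workable form of words, not that ACTT-3 faced equal pressure. Permitting written-policy care is a defensible choice in a pandemic for background treatment. It is harder to defend for the one drug under test.

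A reader might infer that off-study interferon would go unrecorded. The documents do not support that: in-hospital prescription drugs are recorded, interferon is in no exempt class, and biologics cannot be entered just once. Only use after discharge falls outside the recording window. A reader might also infer that controls did receive interferon, or that the power table measures harm from use in category 6 or 7. Neither follows from the documents.

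**Conclusion.** The rule as written makes the post-enrollment ban on off-study interferon depend on local policy, or on the NIH guideline as fallback. It would allow the investigational drug open-label in either arm, including after study injections stop at category 6 or 7. This is a gap in the rule, not a demonstrated exposure; actual use is unknown and may be zero.

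If there were use, the consequence for the primary test would be lost power. Under the assumed dilution, losing 5% of the log ratio leaves power just above 85% at 831 recoveries, and losing 10% takes it below. The point merits a cheap correction and is not a threat to the trial's validity.

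**What to change.** In section 6.5.2, remove interferon from the policy-dependent list and add a rule along these lines: *Off-study interferon of any type for COVID-19 is prohibited through Day 29 in both arms and in all ordinal categories, regardless of local policy or guideline, including after study injections are stopped. Any use is a protocol deviation, and the subject remains in follow-up through Day 29.* Cross-refer from section 6.5.1.

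The cost is one replaced phrase, a short rule and a notice to sites. Existing recording verifies the ban only until discharge; checking from discharge to Day 29 would need one added question at the Day 15, 22 and 29 contacts. The downside is that a site whose written policy calls for interferon could not apply it to enrolled subjects.

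The protocol gives no closing date for ACTT-3. Appendix D (2.1.1 and 8.1.4.2) refers to it in the past tense, which suggests that enrollment may be over. In that case the remaining step is to report recorded off-study interferon by arm, from data already required.
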